Improving anesthesiology care and perioperative outcomes is a growing field encompassing quality improvement and quality assurance, research, and continuing medical education. Multiple consensus initiatives have standardized perioperative endpoints. However, no standard set of metrics exist to evaluate the quality of Canadian anesthesia care delivery.

Objective

Develop a consensus core list of metrics which can be used to evaluate the quality of anesthesia, perioperative care, and acute pain management for adult inpatient non-cardiac surgical patients for use in quality improvement and quality assurance, research, and continuing medical education in the Canadian care context.

Methods

First, the steering committee will conduct a scoping review of the literature to identify candidate metrics, according to Preferred Reporting Items for Systematic Reviews and Meta-Analyses extension for scoping reviews (PRISMA-ScR) and Joanna Briggs Institute methodology for scoping reviews. Metrics will include patient-reported outcome and patient-reported experience measures, quality and safety indicators, process metrics, and Canadian Anesthesiologists' Society recommended practice standards. The search strategy will include English-language articles published or in use within the past seven years (2015/January-2022/March) in 1) MEDLINE, Embase, CINAHL, Web of Science, and Cochrane Database of Systematic Reviews, 2) grey literature, including guidelines, and 3) existing evaluation metrics used by Canadian departments for quality assurance and improvement. Screening and data extraction will be performed by two independent reviewers using Covidence.

Next, following approval from the Research Ethics Board and with written informed consent from participants, a multidisciplinary panel of anesthesiologists, people with lived surgical experience (patients, caregivers), surgeons, nurses, internal medicine and family physicians, hospital administrators, and researchers will iteratively review the list of candidate metrics using a modified Delphi process. Independent voting, using surveys over three rounds, will be used to identify the most important metrics to define the quality of anesthesia, perioperative care, and acute pain management. Additional cycles may be performed if required.

Impact and dissemination

This study will establish a core set of Canadian consensus metrics for evaluating anesthesia, perioperative care, and acute pain management.

Study Protocol

Introduction

Improving anesthesiology care and perioperative outcomes is a growing field encompassing quality improvement and quality assurance, research, and continuing medical education (1). With the scope of anesthesiology practice expanding further into the perioperative domain, a greater focus on postoperative recovery and longer-term outcomes is warranted (2). Multiple consensus initiatives have standardized perioperative endpoints (3–5). However, no core list of metrics exists to evaluate the quality of Canadian anesthesia, perioperative care, and acute pain management in the context of a broad range of existing patient-reported outcome and experience measures, quality and safety indicators, process metrics, and practice standards.

With the increasing adoption of Anesthesia Information Management Systems, Electronic Health Records, and patient-facing virtual care platforms, we have the opportunity to routinely and systematically collect patient-reported and system-collected data to measure anesthesiology performance. By enabling personalized feedback and learning health system approaches, a standardized set of metrics may provide the foundation for further targeted research and interventions to improve anesthesia, perioperative care, and acute pain management for Canadians (1). In this study, we will engage a diverse, multidisciplinary panel to answer the question: what defines quality in anesthesiology, perioperative medicine, and acute pain management in Canada, and how should we quantify it?

Objectives

The overall objective is to develop a consensus list of metrics which can be used to evaluate the quality of anesthesia, perioperative care, and acute pain management for adults undergoing inpatient non-cardiac surgeries that can be used for quality improvement and quality assurance, research, and continuing medical education in the Canadian care context.

The specific metrics will be obtained using the following approach:

1. Obtain a list of candidate metrics through a scoping literature review. For each metric, information will include a) definition(s), b) studies on validity/feasibility and level of evidence, c) timing of measurement, and d) population(s) studied
2. All outcome metrics, as well as process/structure metrics that have limited supporting evidence, will go through a multidisciplinary modified Delphi consensus process, using surveys, to 1) select and mark the importance for each metric, and 2) select a core set of the most important metrics.

Development of a standardized set of core metrics to assess the quality of anesthesia, perioperative care, and acute pain management in Canada: scoping review and multidisciplinary consensus Delphi study

Methods

Study Design Overview

First, the steering committee will conduct a scoping review of the literature to obtain a list of metrics that have been validated and/or are in clinical use to evaluate anesthesia, perioperative care, and acute pain management, to use as a starting point for the modified Delphi process. Then, following approval from the University of British Columbia Research Ethics Board and with written informed consent from participants, a multidisciplinary panel will identify the most important metrics using a modified Delphi process, in accordance with existing literature including the Core Outcome Set-STAndards for Development (The COS-STAD) recommendations (3,6–11). In the last Delphi cycle, the panel will be asked to select the most essential items into a core set of metrics.

Stage 1. Scoping Review

We will first conduct a scoping review according to the Preferred Reporting Items for Systematic Reviews and Meta-Analyses extension for scoping reviews (PRISMA-ScR) (12) and the Joanna Briggs Institute methodology for scoping reviews (13). The purpose of this scoping review is to explore the evidence on the use of metrics to assess the quality of anesthesia, perioperative care, and acute pain management as reflected in the literature. A scoping review has been selected as the methodology of choice for this review because standardized metrics in perioperative care are an emerging area of research. The scoping review was registered on 2022-03-21 as <https://doi.org/10.17605/OSF.IO/8BNVW>.

Search strategy

The metrics included in our scoping review are patient-reported outcome and patient-reported experience measures, patient satisfaction, quality indicators, safety indicators, practice guidelines, process metrics, and other existing metrics. An initial search (Appendix 1) of MEDLINE (Ovid) was co-developed with guidance by a research librarian ([name]).

The search strategy for this review aims to identify both published and unpublished studies. A three-step search strategy will be utilized. An initial limited search of MEDLINE (Ovid) will be undertaken followed by an analysis of the text words contained in the titles and abstracts, and of the indexed terms used to describe the articles. A second full search strategy using all identified keywords and indexed terms will then be undertaken on MEDLINE (Ovid) and across all other databases. The other databases to be searched will include MEDLINE (Ovid), Embase (Ovid), CINAHL (EBSCOhost), Web of Science, and Cochrane Database of Systematic Reviews (Ovid). Third, the reference list of all identified reports and articles will be searched for additional studies.

Studies from 2015/Jan-2022/March will be considered for inclusion in this review. This start date was chosen because end of 2014 was the end date of the last comprehensive searches in this area from previous studies (4,14). Only articles published in English will be included because of a lack of resources for translating non-English articles. Also, grey literature including guidelines, and existing evaluation metrics used by Canadian departments for quality assurance and improvement will be searched.

Development of a standardized set of core metrics to assess the quality of anesthesia, perioperative care, and acute pain management in Canada: scoping review and multidisciplinary consensus Delphi study

Inclusion criteria:

- Human adults

Note that this was conducted using search terms that excluded journal names in the field of pediatric patients. First, the filters for “adult” are not the same for all databases that will be searched. For instance, the limit for adult on MEDLINE (Ovid) is age 19+ years and Embase (Ovid) is 18 to 64 years. Second, we found that some articles were not indexed by the age filter, which we did not wish to miss. As such, we will manually filter for articles with an adult age group (18+).

- Must involve surgical patients requiring the presence of an anesthesiologist for anesthetic care, specifically for inpatients undergoing non-cardiac surgery.

Note that cardiac surgery is not included as an exclusion in the search strategy but rather will be manually excluded during screening, as we found using search filters excluded non-cardiac surgeries.

- Must include at least one metric, with at least one definition for the metric. We will include patient-reported outcome and patient-reported experience measures, Canadian guidelines, and Canadian Anesthesiologists’ Society recommended practice standards. *Since there is an ongoing umbrella review registered on PROSPERO (15), we excluded quality indicators from the database search strategy and will use the results directly from the review. Since the umbrella review only included systematic reviews and may not account for metrics in recent guidelines and clinical use, we will include quality indicators from our grey literature search.*

- Published or in clinical use within the past 7 years (2015/Jan to 2022/March), to focus on contemporary metrics and because end of 2014 was the end date of the last comprehensive search in this area (14).

Note that only the latest version of guidelines will be included.

- For published studies only: full-text articles, study types being only experimental and epidemiological study designs (including randomized control trials, non-randomized control trials, quasi-experimental studies, before and after studies, prospective and retrospective cohort studies, case-control studies, and analytical cross-sectional studies), scoping/systematic review, and/or meta-analysis.

Exclusion criteria:

- For published studies only: we will exclude articles that are case reports, case series, letters, opinion pieces, commentaries, or editorials.

Due to the availability of multiple reviews and consensus guidelines, these article types will likely not contribute relevant additional information that is not already covered by other included sources. Study protocols are not excluded as they may contain metrics being used in contemporary original research.

- Studies reporting on ambulatory or outpatient surgery (i.e., those who do not require at least an overnight stay).
- Articles published in a language other than English.

Development of a standardized set of core metrics to assess the quality of anesthesia, perioperative care, and acute pain management in Canada: scoping review and multidisciplinary consensus Delphi study

Grey literature search:

Since there exist multiple reviews on perioperative process and structure quality indicators to leverage, which included grey literature searches themselves, we will not perform grey literature search on these metrics. Instead, we will search websites of anesthetic and surgical societies in Canada, United States, United Kingdom, and Europe for guidelines and standards, and include existing standards from the Multicentre Perioperative Outcomes Group (MPOG) (published in 2015/Jan-2022/March as per above).

Sources of guidelines to be searched will include:

- CPG Infobase (<https://joulecma.ca/cpg/homepage/>)
- ECRI Guidelines Trust (<https://guidelines.ecri.org/>)
- Guideline Central (<https://www.guidelinecentral.com/guidelines/>)
- Guidelines International Network (<https://g-i-n.net/>)
- TRIP database (<https://www.tripdatabase.com/>)

Existing metrics used in Canada:

We will contact all Canadian anesthesiology departments as listed in a recent national survey (16) through the Canadian Anesthesiologists' Society (e.g. Association of Canadian University Departments of Anesthesiology (ACUDA) and the electronic mailing list to department heads) and individually to obtain lists of metrics already being used to measure anesthesia, perioperative care, and acute pain management by email, with up to a maximum of two follow-up attempts by email. Departments will not be identified in which metrics they capture in their institutions.

Inclusion and exclusion of metrics

Based on previous literature, there are >200 potential metrics. In order to narrow down to a logically manageable list of candidate metrics (approximately 50 prior to Cycle 1 of Delphi), we will use the following objective criteria.

Inclusion:

- The Delphi panel is most useful when evidence is limited. If there is a high level of trial evidence supporting a process indicator for influencing outcomes (e.g., Grade 1a), the metric will be part of the final metric (including core metric) lists without going through the Delphi cycles. Participants will be informed about these metrics at the start of the questionnaire for each Delphi Cycle.
- Since research in patient-reported outcome and patient-reported experience measures is limited, we will include these metrics regardless of level of evidence.
- Process metrics must have direct anesthesiologist involvement according to the standard of care.

Exclusion:

- Metrics specific to a certain surgery (i.e., not generalizable to the average patient undergoing inpatient surgery).

Development of a standardized set of core metrics to assess the quality of anesthesia, perioperative care, and acute pain management in Canada: scoping review and multidisciplinary consensus Delphi study

- Structural indicators that cannot be changed at an individual and/or departmental level (e.g., availability of blood bank near a hospital). Structural indicators may be reflected in other metrics and can be examined during root cause analysis.
- The process or structure indicator has strong evidence (Grade 1a) for lack of difference in patient or system outcomes.

Article selection

All articles found from the database searches will be uploaded into Covidence (Veritas Health Information, Melbourne, Australia) and duplicates will be removed. Titles and abstracts will be screened by two independent reviewers based on the inclusion/exclusion criteria for eligibility. Selected articles from screening will be retrieved in full-text and assessed by two independent reviewers against the inclusion/exclusion criteria to select studies for data extraction. Disagreements between reviewers will be resolved through discussion, and if not resolved, additional reviewer(s) will be involved in the discussion until a consensus is achieved. The search, screening, inclusion, and exclusion process will be reported in a final scoping review and demonstrated on the PRISMA flow diagram (12).

Data Extraction

Two independent reviewers will extract data from each article using a standardized data extraction form in Covidence that can be exported to Excel for further analysis (Appendix 2), including details about the participants included (cohort characteristics), methodology (definition(s) of metrics, validation of metrics, timing of measurement), and any other data relevant to the review questions (e.g., feasibility of implementation). Disagreements between reviewers will be resolved through discussion, and if not resolved, additional reviewer(s) will be involved in the discussion until a consensus is achieved. If required, the steering committee will contact authors for missing data, with up to a maximum of two attempts by email. If a systematic review is retrieved for a category of metrics, data will be directly extracted from the review, and only articles published after the search date of the review articles will undergo data extraction since the previous articles were likely already included. A draft data extraction form (Appendix 2) will be piloted on two studies and revised if needed and reported in the final manuscript.

Scoping review data analysis and presentation

The results of the scoping review will be synthesized narratively, in the form of tables and text, and supporting data will be directly extracted from the included studies or reports. For each metric, we will report definition(s) of metrics, type of metric per Donabedian category (structure, processes, and outcomes), validation, timing of measurement, number of patients and population studied, feasibility, type(s) of study. The steering committee may also group the metrics into specific themes or domains (e.g., patient comfort).

Metrics may be grouped together amongst similar metrics if their definitions were deemed sufficiently similar as agreed per consensus amongst the steering committee. Patient-reported measures will be grouped by the outcome or experience of interest with a list of the specific measures, rather than the measures as individual items (for example, quality of recovery instead of the specific Measuring quality of recovery-15 (QoR-15) scale).

Development of a standardized set of core metrics to assess the quality of anesthesia, perioperative care, and acute pain management in Canada: scoping review and multidisciplinary consensus Delphi study

The steering committee will work with the patient partner and the patient advisory group to ensure that the language describing the metrics is understandable to a general audience with at least grade six education, particularly for the process metrics. Within the Delphi survey, for each metric there will be a brief description of what it is and why it might be important, and expandable links for further explanation and details for each metric (e.g., the items for a patient-reported outcome or experience measure), as deemed necessary by the steering committee.

Stage 2. Modified Delphi consensus process

Study Population

We aim to recruit 77 participants with the following characteristics (accounting for 30% attrition rate (9,17)):

- 26 anesthesiologists
- 26 patients and/or their family members/caregivers
- 9 surgeons, one from each of the following specialties (may include clinician-researchers):
 - General surgery
 - Neurosurgery
 - Obstetrics and gynecology
 - Orthopedic surgery
 - Otolaryngology
 - Plastic surgery
 - Thoracic surgery
 - Urology
 - Vascular surgery
- 4 nurses
- 8 physicians: 2 each from internal medicine, emergency department, family practice, family practice anesthetists
- 4 health administrators or quality improvement leads

Inclusion Criteria: Adult participants aged 18 and above will be included. Patient/family participants must have undergone a surgical experience within the past three years, and have the capacity to provide informed consent. All other participants must be actively practising in Canada in the disciplines they represent.

Exclusion Criteria: Participants with self-declared conflicts of interest with this project.

While the study will primarily be conducted in English using BC Children's Hospital Research Institute's REDCap survey system (18,19), to ensure representation, participants will not be excluded based on language or technology limitations. During recruitment, patients could indicate accommodations required, including translation and submitting study materials through postal mail. The steering committee will review the degree to which accommodations would be feasible within the human resources and study budget.

Development of a standardized set of core metrics to assess the quality of anesthesia, perioperative care, and acute pain management in Canada: scoping review and multidisciplinary consensus Delphi study

Recruitment, consent, panel selection, and withdrawal

We aim to recruit a geographically and culturally diverse sample of participants that is representative of the Canadian population and care settings, following principles of equity, diversity, and inclusion (EDI). We will aim to recruit broadly to obtain representation in areas including but not limited to: provinces and territories across Canada, gender, indigenous communities, visible minority groups, urban vs. rural, academic vs. community, anesthesia and surgical subspecialties, and surgical procedures.

Information about the Delphi study will be distributed through multiple channels (2) including Canadian department administrators, Canadian Anesthesiologists' Society mailing lists, Perioperative Anesthesia Clinical Trials group, hospital and provincial support for patient oriented research (SPOR) organizations, established patient engagement platforms (e.g. REACH BC, an established patient research engagement and recruitment platform for BC's health authorities and partner universities), social media (Twitter, Facebook, Instagram), patients in participating hospitals, who granted permission to contact for research purposes, and targeted contact of pre-identified participants.

We request waiver of the requirement for a formal informed consent process as the data for this minimal risk behavioural study is collected exclusively using surveys. With respect to TCPS2 3.7A: a) this research represents a minimal risk to our participants; b) the alteration to the consent process is unlikely to affect the welfare of our participants adversely; c) it would be impracticable to conduct the research if we adopted a formal consent process (involving scheduling phone calls with participants, mailing or emailing consent materials to review beforehand, following up with an electronic consent form), especially as we expect our participants to be distributed across multiple time zones in Canada; d) the initial survey (study information and eligibility check) explains that participants are not required to complete it or any subsequent surveys and we propose that this is sufficient to imply consent, as it is typical for survey-based research; and e) there will be no plan to debrief participants, but at each stage they can email the steering committee to request that their data be withdrawn up to the start of the next Delphi round.

Interested participants will be invited to complete a study information and eligibility check survey in REDCap, which will be available via a shared public link. This survey will present study information that will allow them to confirm their eligibility, and establish their willingness and ability to participate, before submitting their preferred contact email address, which will be used to route all subsequent surveys.

Participant data will be de-identified using study ID throughout the study. The participant will be informed that de-identified results from the eligibility survey will be collected to report the study inclusion/exclusion flow, and that if they do not want these data collected then they should not fill the eligibility survey.

A participant can withdraw from the study and/or their consent to data sharing for research at any time. If this happened prior to the start of the Delphi Round 1, the research team will attempt to recruit replacement(s) if possible.

Development of a standardized set of core metrics to assess the quality of anesthesia, perioperative care, and acute pain management in Canada: scoping review and multidisciplinary consensus Delphi study

Participants who completed all components of the study (demographics survey and Delphi) will each receive an electronic gift card of \$75 by email as honorarium); those who only complete the initial round will receive an electronic gift card of \$25.

Full demographics survey

After providing electronic informed consent, a full demographics survey will be sent to each participant for completion within two weeks. This is based on previous methodology and will include age (in decades), sex, gender, race/ethnicity, and geographical category (urban, semi-urban, rural) of hospital they most frequently interact with for the purposes of surgeries. For patients and/or family members only, we will also ask about their highest education level (grade school, high school, diploma or undergraduate degree, postgraduate degree), income (by Canadian tax brackets), ethnicity, home community location if different from the hospital location (urban, semi-urban, rural), occupation, and type(s) of surgery. For health professionals, we will also ask about primary practice area, years in practice (<5, 5-9, 10-19, >20 yrs), subspecialty training, practice setting (academic, community), and involvement in any of research, quality assurance/improvement, or teaching continuing medical education.

Delphi process

The multidisciplinary panel of participants will iteratively review the list of candidate metrics using a modified Delphi process. While specific guidance on consensus thresholds and the optimal scales are limited, the design will follow best practices from literature (3,6-11). In the last Delphi cycle, the panel will be asked to select the most essential items to include into a core set of metrics.

Independent, anonymous voting using REDCap over three rounds will be used to identify the most important metrics to define the quality of anesthetic care. Each round will be coordinated through the Department of Anesthesiology, Pharmacology and Therapeutics, Faculty of Medicine, UBC.

Participants will be given at least two weeks of notice about an upcoming round, and will have two weeks to complete the REDCap survey for a given round. Reminder emails will be sent 7 and 14 days after the survey opens to those who have not yet completed it. If a survey is still not completed, up to two additional reminders will be sent once a week, and if still no response, the round will be closed. The participant who missed a round will still be able to participate in future rounds. There will be at least two weeks between each round to provide time for the steering committee to analyze the data and prepare for the next round. Additional cycles (beyond the 3rd) may be performed if the objectives have not been achieved.

Delphi Round 1

The initial list of metrics and descriptions from the scoping review will be presented. Participants will independently score each of the listed metrics for importance on a five-point scale (from '1=not at all important' to '5=very important') (8). Participants may also enter comments in free-text if they have any specific feedback or suggestions on a given item, which will be summarized and shared with participants in Round 2. The mean and median scores for each metric will be calculated for overall panel and for subgroups of 1)

Development of a standardized set of core metrics to assess the quality of anesthesia, perioperative care, and acute pain management in Canada: scoping review and multidisciplinary consensus Delphi study

patient/caregiver and 2) health provider groups, and will also be presented in Round 2. Metrics receiving a mean score ≥ 4 by $\geq 65\%$ of each subgroup and ≤ 2 by $<20\%$ of the subgroups will be retained for voting in Round 2 (8).

Delphi Round 2

Participants will score each metric using the same scale as in Round 1, and suggest revisions or comments as needed. Metrics receiving a mean score ≥ 4 by $\geq 65\%$ of each subgroup and ≤ 2 by $<20\%$ of the subgroups will be retained for voting and prioritizing in Round 3.

Delphi Round 3

Prior to Round 3, the study team will review the list of metrics, and aggregate and/or refine their wording as needed. Participants will be presented with a list of metrics with mean and standard deviation scores from the Likert scales, and be asked to vote on which metrics consist of a core set of problems (i.e., must be addressed by the health system as a priority) using a three-point scale of “definitely priority”, “equivocal (either way)”, and “not a priority” (10,20). Metrics where $>70\%$ participants voted “definite” will be marked in the publication as the core metric set. If no consensus is reached, there may be additional rounds of rating using a smaller sample of participants.

Statistical analysis

Analysis will be performed using R (R Foundation for Statistical Computing, Vienna, Austria). Cohort characteristics will be reported using descriptive statistics. Each round of Delphi will be analyzed as described above, and presented both as an overall group and as individual subgroups.

Sample size calculation

There is limited guidance regarding sample size for Delphi processes, but, in general, the key is to choose a broad representation from key stakeholders with a margin of safety built in for possible attrition. Delphi studies often involve a total of 17 members (9) and that adding more participants above 23 did not alter the consensus results (21). We have aimed for broad representation across all the key stakeholder groups. Thus, we chose $n = 20$ for each of the groups of anesthesiologists and patients. We chose the number of surgeons to represent the primary set of noncardiac surgical specialties. We also accounted for an attrition rate of 30% per literature (9,17) to ensure that there will be sufficient representation in the last cycle despite attrition.

Impact and future directions

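### Does the date limit in the Grey literature search section shut out pre-2015 standards that are still in use, against the inclusion criteria?

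*Combined protocol and SAP*

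**What the plan says.** The January 2015 to March 2022 window is stated in four places in the combined protocol and SAP.

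- **Abstract, Methods:** the search takes "articles published or in use within the past seven years (2015/January-2022/March", and the list that follows covers databases, grey literature and departmental metrics.
- **Search strategy:** "Studies from 2015/Jan-2022/March will be considered for inclusion in this review". The same paragraph then adds that "grey literature including guidelines, and existing evaluation metrics used by Canadian departments for quality assurance and improvement will be searched".
- **Inclusion criteria:** "Published or in clinical use within the past 7 years (2015/Jan to 2022/March". A note beneath keeps only the latest version of a guideline.
- **Grey literature search:** the team will "include existing standards from the Multicentre Perioperative Outcomes Group (MPOG) (published in 2015/Jan-2022/March as per above". Guidelines and standards from societies in Canada, the United States, the United Kingdom and Europe come earlier in the same sentence.

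On quality indicators, the Inclusion criteria leave them out of the database search because an umbrella review will supply them. They add that, as that review "may not account for metrics in recent guidelines and clinical use, we will include quality indicators from our grey literature search". The Grey literature search section opens "Since there exist multiple reviews on perioperative process and structure quality indicators to leverage, which included grey literature searches themselves" and continues "we will not perform grey literature search on these metrics". It then names society and outcomes-group sources as what will be searched instead.

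**The concern.** Two statements seem to pull apart.

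**Dates.** The abstract and the inclusion criteria offer two ways in, publication or use during the window. The grey literature section mentions only publication. Someone applying the inclusion criteria would keep a pre-2015 outcomes-group standard still in use. Someone applying the grey literature sentence literally would reject it.

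**Quality indicators.** One section says they will be taken from grey literature, and another says no such search will be run for process and structure indicators. Taken alone, the second seems to close the route that the first relies on.

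At stake is the candidate list that goes to the Delphi panel. A metric missed here might not be recovered, and process indicators with Grade 1a evidence pass from this stage to the final and core lists without a vote.

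**Working it through.** There is no sample size, power or error-rate figure to reproduce. The check sets the texts side by side.

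**Step 1. Count the statements.** Of the four date statements, the one in Search strategy concerns studies. The other three (abstract, Inclusion criteria, Grey literature search) apply to grey items. Two of the three carry the in-use route, so 3 − 2 = 1 does not. The calendar window is the same in all four. The count shows where the wording differs, not which rule governs.

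**Step 2. Find where the rules disagree.** Compare the inclusion criterion with the literal grey literature sentence:

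- published in the window: eligible under both;
- published before 2015 and not in use in the window: ineligible under both;
- published before 2015 and in use in the window: eligible under the first, ineligible under the second.

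Only the third case differs.

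**Step 3. Ask which rule governs.** The limit refers to something above it, so it does not stand alone. Two earlier statements in the Methods could be meant. The one in Search strategy speaks of studies, which an outcomes-group standard is not. The one in Inclusion criteria is the formal eligibility rule and already contains the in-use route. The sentence also describes the standards as existing, which fits current use. The Study Design Overview gives the aim as metrics that are validated, in clinical use, or both. The natural reading is therefore an abbreviated inclusion criterion.

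**Step 4. Suppose the literal reading was meant.** A publication limit would have some support in the plan. The 2015 start was chosen because the last comprehensive searches ended with 2014. Older items could still enter by four routes:

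- earlier process and structure reviews, which the plan says had their own grey literature searches;
- the umbrella review of quality indicators;
- the Canadian society practice standards, named in the Inclusion criteria;
- departmental lists, for which no publication-date limit is stated where they are requested.

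What remains is a pre-2015 standard, in use during the window and absent from all four. The documents do not show that one exists.

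**Step 5. Quality indicators.** The sentence declining a search is followed at once by the sources that will be searched in its place, and the departmental request comes soon after. Search strategy lists guidelines and departmental metrics as grey sources. The analysis section reports every metric as structure, process or outcome. The Appendix 2 form offers guideline and departmental metric as publication types and codes the same three categories. Under one reading all of this fits: no dedicated search for process and structure indicators is run, and indicators found in the named sources are extracted.

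**The case for a change.** The best case for a change is that the written rule carries more weight for grey sources than for articles. The Article selection section describes two independent screeners and a way to settle disagreements for articles from the database searches, and states no equivalent for grey items. The Delphi rounds invite comments on listed metrics but state no route for adding one that the review missed. The credit given to earlier grey literature searches covers process and structure indicators, not outcome standards. The limit might also reach society guidelines, where a latest version dated before 2015 and still in use is the disputed case. The repair would be a few words.

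Part of this stands. The sentence does not repeat the in-use route, its back-reference could have been more exact, and its reach within the sentence is ambiguous. But these points show why a lost metric would matter, not that one is lost. No section gives grey items a separate eligibility list, so the inclusion criteria are the rule to apply. The Article selection section also commits the team to reporting its search, inclusion and exclusion process, so the rule used can be stated. A remedy that accepts either rule, provided it is named, does not identify an error in the design.

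**Conclusion.** No change is needed. On dates, the plan has a loose cross-reference that a sensible team would resolve through its own inclusion criteria. On quality indicators, the sections agree when read together.

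The wording gap is firm for one source, the outcomes-group standards, and possible for society guidelines and standards from four regions. The number of metrics involved cannot be derived and is probably small. No result, threshold or conclusion is shown to change.

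This rests on two assumptions: that the back-reference points to the inclusion criteria, and that indicators met in the named grey sources are extracted as the Appendix 2 form allows. Confidence in the first is moderate, because the text also permits the literal reading. A pre-2015 standard in use during the window, missing from every other route and rejected on publication date alone, would make the point matter. The documents give no sign of one.
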